4 STUDY INTERVENTION

4.1 Intervention

Arm (1) (reference arm)

- Screen-negative: If the total-PSA level is “normal”, i.e. below the cut-off 3.0 ng/mL, no further testing or examination will be performed, but all men will be re-invited.
- Screen-positive: If the total-PSA level is “elevated” above the cut-off i.e. ≥ 3.0 ng/mL, the man will be invited for an MRI.

All men will be recommended standard biopsy, i.e., digital rectal exam followed by TRUS-guided 12-core standard prostate biopsy according to the screening protocol. These standard biopsies will be taken with both the urologist and subject blinded to the MRI result. After these standard biopsies, the study nurse will show the urologist the result from the MRI examination, and in case of suspicious lesion at MRI, 3-4 targeted* biopsies in each of these lesions will be performed in the same séance; 3 targeted biopsies if one of the systematic biopsies already hit the area, and 4 targeted biopsies if otherwise.

- Men in whom MRI for any reason is not achievable or the result is inconclusive will only undergo systematic biopsies

Arm (2) (first experimental arm)

- Screen-negative: If the total-PSA level is “normal”, i.e., below 3.0 ng/mL, no further testing or examination will be performed. The man will be re-invited for screening identical to Arm (1).
- Screen-positive: If the total-PSA level is “elevated” ≥ 3.0 ng/mL, he will be offered MRI.
 - If the MRI is positive (PI-RADS 3-4), only targeted* biopsies will be performed, i.e. 4 biopsy cores targeted against each suspicious lesion, but no systematic biopsies.
 - If the MRI is positive (PI-RADS 5), targeted* biopsies will be performed, i.e., 4 biopsy cores targeted against each suspicious lesion but also systematic biopsies. Changed 2018-10-15 (see amendment 5)
 - If the MRI is negative no biopsies will be performed.
 - If the MRI is negative and PSA ≥ 10 and PSA density (PSAD), ≥ 0.1 , systematic 12-core biopsies will be performed. PSA cut off changed 2016-03-01 from 20 to 10 ng/mL (see amendment 1).
 - Men in whom MRI for any reason is not achievable, or the MRI is technically inferior (for example in men with hip prosthesis), are invited for urological examination with digital rectal examination (DRE) and transrectal ultrasound

(TRUS). These men are included in the intention to screen analysis but not in the per protocol analysis (see 6.2.1).

Arm (3) (experimental arm II)

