6 STATISTICAL CONSIDERATIONS

6.1 Sample Size Calculation

The hypothesis is that the MRI-targeted biopsy only strategy would reduce insignificant cancer with 50%. Based on previous studies and expert knowledge, we assumed that the proportion of men diagnosed with insignificant cancer among men with PSA ≥ 3 in Arm 1 (reference arm) would be 9%. This gave a sample size of N=1,164 men with PSA ≥ 3 ng/mL to achieve 80% power, when having a two-sided test alternative and significance level 5%. Furthermore, we hypothesized that 7% among men attending PSA-screening would have an elevated PSA and that the participation rate would be 50%, which lead to the sample size N=33,260 altogether in the three screening-arms. Accounting for uncertainty in the hypothesized proportion of insignificant cancers and in the proportion of men with PSA ≥ 3

ng/mL among those screened, lead to the final sample size of N=36,000 for the SG. With an allocation rate of 1:2 between the CG and SG, altogether, N=54,000 men are needed to be included in the study.

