6.2 Analysis plan for the primary and secondary endpoints

6.2.1 Primary objective (Detection of insignificant cancer)

- Hypothesis

The proportion of men with insignificant cancer detected by PSA testing with threshold 3 ng/mL, systematic biopsies and MRI-targeted biopsies (p_1) will be different from the proportion detected when omitting systematic biopsies (p_2):

H_0 (null hypothesis): $p_1 = p_2$

H_A (alternative hypothesis): $p_1 \neq p_2$

Although the hypothesis of the investigators is one-sided, that MRI-targeted biopsies only will lower the proportion, the test is two-sided to allow for a significant effect in both directions.

- Analysis populations

First assessment (after completion of screening round 1): All men in arm 1 will be compared to all men in arm 2 and 3 combined. However, for men in arm 3, cancers detected in men with PSA < 3 ng/mL will be ignored.

Later assessments: the analysis will compare all men in arm 1 with all men in arm 2.

The analyses will primarily be carried out according to the intention to treat (ITT) principle, which here means that all men will be included in the analysis and belong to the arm they were allocated to, irrespective of whether they completed the intended diagnostic pathway with MRI and biopsies or not.

Furthermore, per protocol analyses will be carried out including only men who strictly follow the protocol.

An additional analyses will compare men in arm 1 who underwent MRI followed by systematic and possible targeted biopsies (if MRI positive) with those in arm 2 and 3 who underwent MRI and also targeted biopsies but ignoring results from possible systematic biopsies if those were taken at the primary biopsy and the targeted biopsies were benign.

- Analysis

Outcome measure is the relative difference of the proportion of insignificant cancers detected in arms 2 and 3 combined vs arm 1 (the cancers detected in men with PSA below 3 ng/mL in arm 3 will be ignored). In later assessments only arm 1 and 2 will be included. The result will be presented as a point estimate with a two-sided 95% confidence interval, and a p-value of the hypothesis test. Significance testing will only be carried out for the first definition of insignificant cancer (Gleason grade 3+3). The score method will be used for testing and confidence intervals (27). A p-value below 5% will be considered statistically significant.

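### The additional analysis keeps MRI-negative men in arm 1 but drops them from arms 2 and 3, so its ratio is biased upward and a true halving reverses if under half of MRIs are positive

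*Protocol*

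**What the plan says.** Under 'Analysis populations', protocol section 6.2.1 names three analyses. The first is intention to treat, with every man in the arm he was allocated to. The second is per protocol. The third is an additional analysis with its own population rule.

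- **Arm 1 side:** men who had MRI and then systematic biopsy, with targeted cores only where the MRI was positive. MRI-negative men therefore stay in.
- **Arm 2/3 side:** the comparison is "with those in arm 2 and 3 who underwent MRI and also targeted biopsies but ignoring results from possible systematic biopsies", the systematic results being ignored when they came from the primary biopsy and the targeted cores were benign. The condition on a positive MRI that appears for arm 1 is not repeated.

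Section 4.1 settles who can have targeted cores. Its footnote defines targeted biopsy as aimed at MRI-positive areas. For arm 2 it says: "If the MRI is negative no biopsies will be performed". The stated exception, PSA ≥ 10 with PSA density ≥ 0.1, leads to systematic cores and not targeted ones. Arm 3 is identical apart from its PSA cut-off. Section 6.2.2 analyses significant cancer in the same way as insignificant cancer, but without hypothesis testing.

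**The concern.** Sparing MRI-negative men a biopsy is a central part of the strategy under test (section 3). Read literally, the rule removes exactly these men from the experimental side and keeps their counterparts in the reference side. Dividing the arm 2/3 cancers by MRI-positive men alone inflates that proportion by 1/q.

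For insignificant cancer this shrinks or reverses the benefit the trial is looking for. For significant cancer it works the other way: it flatters the experimental arms on the question whether detection is maintained. A prespecified supplementary result that appears to contradict the primary result, or that wrongly reassures on the secondary one, would be hard to explain afterwards.

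**Working it through.** **Inputs from protocol section 6.1.** The insignificant-cancer proportion "among men with PSA ≥ 3 in Arm 1 (reference arm) would be 9" per cent. The hypothesis is that "the MRI-targeted biopsy only strategy would reduce insignificant cancer with 50" per cent, which gives 4.5% in arms 2 and 3. The size is "N=1,164 men with PSA ≥ 3 ng/mL to achieve 80% power", "when having a two-sided test alternative and significance level 5" per cent. Section 3.5 allocates 1:1:1, so arm 1 against arms 2 and 3 combined is 1:2.

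**Assumption.** q is the share of men with PSA ≥ 3 ng/mL whose MRI is positive. The protocol does not state it, so a range is shown.

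**Reproducing the plan's figure.** Two proportions, 9% against 4.5%, 1:2, two-sided 5%, 80% power, continuity-corrected: 382 men in arm 1 and 3 × 382 = 1,146 in total, 1.5% below the stated 1,164. Other variants give 1,050 (no correction) and about 1,202 (unpooled variance). Men to invite: 1,164 / (0.07 × 0.50) = 33,257, against the stated 33,260. The 9% and 4.5% are therefore proportions of all men with PSA ≥ 3 ng/mL, MRI-negative men included.

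**Literal populations.** Split 1,164 as 388 and 776. Assume that every man completes his pathway and that all arm 2/3 cancers are found on targeted cores.

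- Arm 1: 0.09 × 388 ≈ 35 cancers among 388 men = 9.0%.
- Arms 2/3: 0.045 × 776 ≈ 35 cancers among 776 × q men = 4.5%/q.
- Apparent ratio = (0.045/q) / 0.09 = 0.50/q. For a true ratio R it is R/q, so the direction reverses when q < R.

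| q (assumed) | Arm 2/3 men counted | Arm 2/3 proportion | Apparent ratio |
|---|---|---|---|
| 0.20 | 155 | 22.5% | 2.50 |
| 0.30 | 233 | 15.0% | 1.67 |
| 0.40 | 310 | 11.3% | 1.25 |
| 0.50 | 388 | 9.0% | 1.00 |
| 0.60 | 466 | 7.5% | 0.83 |
| 0.70 | 543 | 6.4% | 0.71 |
| all MRI-examined men kept | 776 | 4.5% | 0.50 |

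**Could the reversal look significant?** Take q = 0.30, 35/388 against 35/233. The pooled proportion is 70/621 = 0.113 and the standard error is √[0.113 × 0.887 × (1/388 + 1/233)] = 0.026. Then z = 0.060/0.026 ≈ 2.3, nominal p about 0.02 in the wrong direction.

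**Significant cancer.** Suppose a true 20% loss of detection (R = 0.8, chosen for illustration) and q = 0.40. The apparent ratio is 0.8/0.40 = 2.0, and the loss shows as a doubling.

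**Arm 3 men with PSA 1.8–2.99 ng/mL.** Their cancers are ignored, but the sentence does not say whether the men stay in the denominator. Suppose they do, with m such MRI-examined men per arm 3 man with PSA ≥ 3 ng/mL and the same q. The denominator is 388 × q × (2 + m). With m = 1 and q = 0.40 it is 466, the proportion is 35/466 = 7.5% and the ratio is about 0.83 instead of 1.25. This dilution pulls against the first bias but does not correct it.

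**The case against.** **It is only a supplementary analysis.** This stands. Intention to treat is primary and keeps all men in each arm, so the main result and the sample size are sound. A reader might infer that the primary comparison is compromised; nothing in the protocol supports that.

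**The authors probably meant targeted biopsy if the MRI was positive.** Possibly. But the condition is written for arm 1 only, the sentence sits under 'Analysis populations', and its closing clause presupposes that targeted cores were taken. The intended reading has to be written down.

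**The reversal is not established.** This also stands. A reader might infer that the analysis will show an increase. That needs q below 0.50 under the plan's own effect, and the documents give no q. Keeping arm 3 men with PSA below 3 ng/mL could restore the direction, as shown. Cancers found only on systematic cores in MRI-negative men with high PSA would also leave the arm 2/3 numerator and lower the ratio.

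**Systematic cores still count once targeted cores show cancer.** A reader might call this contamination of a targeted-only comparison. Section 5.1 explains it as deliberate: the later completion cores offset sampling error between two biopsy techniques. Dropping them for grade would set about 4 cores per lesion against 12 plus 3–4 in MRI-positive arm 1 men, a new imbalance. The rule should stay.

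**The per-protocol set.** For arm 2 men without a usable MRI, section 4.1 says "These men are included in the intention to screen analysis but not in the per protocol analysis", while for arm 1 it says "Men in whom MRI for any reason is not achievable or the result is inconclusive will only undergo systematic biopsies" and is silent on exclusion. A reader might infer a second asymmetry. That rests largely on silence about a detail an analysis plan may settle. It does not enter the additional analysis, which requires an MRI on both sides.

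**Conclusion.** The concern holds for the additional analysis in section 6.2.1 as written. Its arm 2/3 side is MRI-positive by construction and its arm 1 side is not, so it estimates R/q and not R. Under the planned halving, the reduction is understated at every q below 1, vanishes at q = 0.50 and is reversed below that; across assumed q of 0.30 to 0.70 the apparent ratio runs from 1.67 to 0.71 instead of 0.50. These figures assume full pathway completion, all arm 2/3 cancers found on targeted cores, and only men with PSA ≥ 3 ng/mL counted. The selection itself follows from the text; the size depends on q, which is unknown here. Through section 6.2.2 the same inflation carries over to significant cancer, where it could conceal a loss of detection.

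**What to change.** Reword the population sentence in section 6.2.1 so that:

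- the arm 2/3 set is men who underwent MRI and, if it was positive, targeted biopsy;
- MRI-negative men in arms 2 and 3 stay in the denominator and count as having no cancer detected by targeted biopsy;
- both sides are restricted to PSA ≥ 3 ng/mL, or otherwise use the same denominator. In practice the restriction affects arm 3 only;
- the section 5.1 rule is kept, so that completion systematic cores count for grade once targeted cores show cancer.

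State that the same set applies to significant cancer. Under the planning assumptions this returns 35/388 = 9.0% against 35/776 = 4.5%, ratio 0.50. The analysis still conditions on completing the pathway, which demands a biopsy of every arm 1 man but not of MRI-negative men in arms 2 and 3, so it should remain supplementary. The cost is one sentence and a change of denominator in the analysis code; no new data are needed.

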2.5 Outcome measures and times of assessments

Details of all outcome definitions and times of assessments are defined in table below.

Outcome definitions and times of assessments for the primary and secondary objectives

Objective	Definition	Time of assessment
Primary	Proportions of clinically insignificant cancers* Arm 1 vs Arm 2+3*	After completion of screening-round 1 (only screening visits in round 1 are analysed). Next assessment includes all screening visits up to 30 th June 2022 and 2, 6 and 10 years thereafter
Secondary	Proportions of clinically significant cancers* Arm 1 vs Arm 2+3*.	After completion of screening-round 1 (only screening visits in round 1 are analysed). Next assessment includes all screening visits up to 30 th June 2022 and 2, 6 and 10 years thereafter
Additional 1)	Proportions of clinically significant cancers Arm 2 vs Arm 3. See separate protocol	Including men who were invited and participated up to 30 th June 2024 and 2, 6 and 10 years thereafter
Additional 2)	Cancer-specific incidence and mortality SG vs CG (intention to screen analysis). See separate protocol	12 years after randomization (31 December 2027) and every third year after.
Additional 3)	Sensitivity and specificity comparing multi- versus bi-parametric MRI. See separate protocol	After completion of screening round 1

SR = screening round. SG = Screening group. CG = control group

* The first analysis based upon screening round 1 will also include men in arm 3 ignoring cancers detected in the PSA range 1.8-2.99 and group them together with men in arm 2, but analysis coming after that including also subsequent screening rounds will only compare arm1 versus arm 2.

The primary definition of clinically significant PC is Gleason¹ Score $\geq 3 + 4$ (also known as Grade Group 2-5) on biopsy but will also be analyzed with other definitions provided in Table page 25.

¹ Gleason grading (after Donald F Gleason 1920-2008) is the pathological grading of prostate needle biopsies. Gleason Score is based on recognizing the two most common morphological Gleason grade/pattern under the microscope, a primary and secondary grade, and then summing the two, e.g. 4+3=7. If there are more than two patterns present, and the worst grade is neither the primary nor the secondary grade, GS is based on the predominant + highest grade. The higher the score, the more aggressive the tumor is.

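### One unadjusted 5% rule covers all five assessments of the primary outcome, and no sentence makes the round-1 comparison the sole confirmatory test

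*Protocol*

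**What the plan says.** The Primary row of the table in Protocol section 2.5 places the first assessment after screening round 1 and continues: "Next assessment includes all screening visits up to 30 th June 2022 and 2, 6 and 10 years thereafter". That makes five assessments: round 1, then 2022, 2024, 2028 and 2032.

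Section 6.2.1 states a single null hypothesis, p1 = p2, and describes two kinds of analysis under it:

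- "First assessment (after completion of screening round 1): All men in arm 1 will be compared to all men in arm 2 and 3 combined" (cancers found in arm 3 below PSA 3 ng/mL are ignored).
- "Later assessments: the analysis will compare all men in arm 1 with all men in arm 2".

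The Analysis paragraph of the same section says "In later assessments only arm 1 and 2 will be included", and the next sentence reads "The result will be presented as a point estimate with a two-sided 95% confidence interval, and a p-value of the hypothesis test". The paragraph ends with "A p-value below 5% will be considered statistically significant". The only limit on testing concerns the endpoint definition: "Significance testing will only be carried out for the first definition of insignificant cancer (Gleason grade 3+3". No limit refers to the time of assessment.

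Other sections bear on which assessment is meant to be primary. Section 3 lists the comparisons possible after round 1 and labels arms 2-3 versus arm 1 as the primary objective. The list for multiple rounds, arm 2 versus arm 1, carries no such label. Section 3.4 explains the changed allocation ratio by the need to evaluate the primary objective at four years, and section 5.1 plans that evaluation in year 4.

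**The concern.** As written, the 5% rule applies at every assessment of the primary outcome. The protocol controls multiplicity in other directions: one definition of insignificant cancer is tested, and section 6.2.2 drops hypothesis testing for significant cancer. It does not do so over time. No alpha is split or ordered across the five assessments.

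The change of contrast adds to the ambiguity. A non-significant round-1 result could be followed by a significant arm 1 versus arm 2 result in a later year, or the reverse. Section 6.2.1 would allow both to be reported as tests of the same null hypothesis at the same threshold. In a trial meant to inform screening policy, the protocol should state which result settles the primary question.

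**Working it through.** **1. Which comparison does the sample size fit?** Inputs from section 6.1: 9% in arm 1, a 50% relative reduction (so 4.5%), 80% power, two-sided 5%, N = 1,164 men with PSA ≥ 3 ng/mL. Round 1 compares one arm with two, so the ratio is k = 2 and the mean proportion is (0.09 + 2 × 0.045)/3 = 0.06.

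n1 = [1.96 √(1.5 × 0.06 × 0.94) + 0.8416 √(0.09 × 0.91 + 0.045 × 0.955/2)]² / 0.045² ≈ 349, rounded up to 350 (total 1,050).

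The continuity correction raises n1 to 382, a total of 382 + 764 = 1,146, which is 1.5% below 1,164. Other versions lie further away: 1:2 unpooled about 1,202, 1:2 arcsine about 1,068, 1:1 uncorrected 974, 1:1 corrected 1,062. The screening-group figure follows: 1,164/(0.07 × 0.50) = 33,257, against the stated 33,260. The sample size therefore fits best the 1:2 comparison, which is used only at the first assessment. The match is close but not exact.

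**2. Error of the first test alone.** It is the earliest test and is made at two-sided 5%. Later testing cannot change its error, and simulation gives 5.0%.

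**3. Error if any of the five tests may support the claim.** With equal arms and no true difference, let I_k be the cumulative information per arm at assessment k, as a share of the final amount. Let B1, B2 and B3 be the cumulative results of the three arms.

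- First test: Z1 = [B1 − (B2 + B3)/2] / √(1.5 I_1)
- Later tests: Zk = (B1 − B2) / √(2 I_k)
- Correlation of the first with a later test: √0.75 × √(I_1/I_k)
- Correlation between later tests j < k: √(I_j/I_k)

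The factor √0.75 = 0.866 comes from the change of contrast. Even with no new information, the second test would not simply repeat the first. As a check, I_1/I_2 = 0.5 gives 0.866 × 0.707 = 0.612, and the simulated correlation is 0.612.

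Each test rejects at |Z| > 1.96, with 1,000,000 replicates per row. The information shares are assumed.

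| Assumed cumulative shares | At least one of five | At least one of first two |
|---|---|---|
| 0.10, 0.20, 0.30, 0.65, 1 | 16.5% | 8.7% |
| 0.10, 0.18, 0.32, 0.56, 1 | 16.7% | 8.6% |
| 0.20, 0.40, 0.60, 0.80, 1 | 14.6% | 8.7% |
| 0.30, 0.40, 0.50, 0.75, 1 | 13.9% | 8.1% |
| 0.40, 0.50, 0.65, 0.85, 1 | 13.1% | 8.0% |
| 0.50, 0.60, 0.70, 0.85, 1 | 12.1% | 7.8% |
| 0.50, 0.80, 0.90, 0.98, 1 | 11.1% | 8.4% |
| 0.60, 0.70, 0.80, 0.90, 1 | 11.2% | 7.7% |
| 0.70, 0.775, 0.85, 0.925, 1 | 10.6% | 7.7% |
| 0.80, 0.85, 0.90, 0.95, 1 | 9.7% | 7.5% |
| 0.90, 0.925, 0.95, 0.975, 1 | 8.9% | 7.5% |

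For comparison, five independent tests would give 1 − 0.95⁵ = 22.6%. Keeping the same two arms throughout would give 14.2% instead of 14.6% for equal steps, and 7.3% instead of 8.9% in the last row.

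**4. After the change.** With round 1 as the only confirmatory test, the error is 5.0%. With 1% at each of five tests, the total is at most 5 × 1% = 5%.

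**The case against.** The strongest reply is that the protocol does show which comparison is primary. Section 3 attaches the label to arms 2-3 versus arm 1 after round 1, sections 3.4 and 5.1 put the evaluation at year 4, and the sample size fits that comparison best. This stands. A reader of section 6.2.1 alone might infer that nothing identifies the deciding assessment, or that the primary test itself runs at 11% to 15% instead of 5%. The documents support neither inference: the design points to round 1, and that test keeps its 5%.

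It can also be said that the later assessments ask another question. They omit arm 3, accumulate repeat rounds and cover a changed pathway: bi-parametric MRI from round 2 (section 5.2), and systematic cores added for PI-RADS 5 lesions, which the table notes in section 5.1 place outside round 1. Whether long-term reports of this kind need a shared alpha is a matter of judgement. That limits how far the five can be treated as repeated looks at one hypothesis, but section 6.2.1 itself puts them under one null hypothesis and one threshold.

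Finally, alpha handling over time may be left to a statistical analysis plan, which was not at hand. That would excuse silence. Here, however, the protocol states a significance rule and does not confine it to the first assessment.

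**Conclusion.** The point holds as a gap between the design's evident intent and its stated rule. Round 1 appears to be the primary evaluation, but no sentence makes it the sole confirmatory test, and section 6.2.1 lets later tests of a different contrast be called significant on the primary objective.

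The inflation is conditional. It requires that any of the five results may support the primary claim and that there is no true difference at any assessment. It also depends on information shares that the protocol does not give: about 11% to 15% for round-1 shares of 20% to 60%, and about 9% to 17% for 10% to 90%. Every scenario examined exceeds 5%, and the need for clarification does not depend on the exact figure. No passage says that a later result would overturn the round-1 result; the protocol simply does not rule it out.

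**What to change.** State in sections 2.5 and 6.2.1 that the round-1 comparison of arm 1 with arms 2+3 is the only confirmatory test of the primary objective, at two-sided 5%. State also that the later arm 1 versus arm 2 assessments will be reported as point estimates with 95% confidence intervals, without a significance claim on that objective. Section 6.2.2 already takes this estimate-only approach for significant cancer.

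If formal claims at later assessments are wanted, allocate alpha across the five instead, for example 1% each. The first test would then run at 1%, and the power in section 6.1, which was set at 5%, would have to be recalculated.

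The first option costs two sentences and changes neither sample size nor conduct. Its small downside is that later assessments lose formal significance claims on the primary objective.
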